6.3 Blinding

Investigators performing data analysis and video raters will be blinded to group allocation by editing audio/video material in such a way that the final end of the scenario, with the occurrence of death or return of spontaneous circulation is not visible. Participants will be blinded to the nature of the study, their group assignment and scenario at the time of enrollment and scenario briefing during the initial and retention test.

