5. DESIGN OF THE CLINICAL INVESTIGATION

This study will be designed as multi center, investigator blinded, randomized, controlled, prospective trial with qualitative and quantitative methodology.

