7.3 Statistical analysis

As it has been suggested as best practice for stratified randomized controlled trials, ANCOVA will be used to analyze the outcome parameters using the level of training (PGY1-3 vs PGY 4-5 and fellows) and specialities (acute care specialities vs. non-acute care specialities) as covariates.³⁵ Group assignment (unexpected death, alive) will be used as the independent variable. Demographic data will be analyzed using an unpaired Student's *t*-test or chi-square test, where appropriate.

Curved/linear regression analysis will be performed to assess the correlations between each outcome and stress as well as emotions. As it is common practice, results of Likert-like scales will be treated as interval-measures and thereby analyzed by using parametric tests.^{36,37}

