7.4 Qualitative analysis

Qualitative data will be analyzed according to grounded theory by sorting, coding and redefining into emergent topics. Thereafter interview transcripts will be compared against each other.^{38,39} By using an iterative approach, ongoing preliminary analysis of the results gathered by the semi-structured interviews will lead to adaptation of the interviews. Thereby thematic categories will be established and continuously refined. This process will be performed until coding results in an explanation of the observations, and saturation is reached.

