Impact of Unexpected Death in Simulation: Skill Retention, Stress and Emotions

Data Analysis Plan

Primary Outcome: Difference in retention of non-technical crisis resource management (CRM) skills using Ottawa Global Rating Scale (OGRS)

ANCOVA:

- Dependent variable: OGRS score (total score)
- Independent variable: Death vs. survival
- Covariates: Junior vs. senior; Acute vs. non-acute

Secondary Outcome 1: Technical CRM skills (according to checklist)

- Same Videos to be provided for primary outcome will be scored using the “Task-specific checklist” (derived from American Heart Association’s Megacode Checklist) and given a score out of 18

ANCOVA:

- Dependent variable: Task-specific checklist score (total score)
- Independent variable: Death vs. survival
- Covariates: Junior vs. senior; Acute vs. non-acute

Secondary Outcome 2: Stress

Measure 1: Salivary cortisol

Five time points (minutes passed since baseline):

1. Baseline (0 minutes) during the accommodation period at the beginning of the day
2. Before scenario (10 minutes)
3. Immediately after scenario (30 minutes)
4. 30 minutes after start of scenario (45 minutes)
5. After debrief (50 minutes)

ANCOVA:

- Dependent variable: Change in cortisol concentration (versus baseline) at a given time point (for each time point)
- Independent variable: Death vs. survival
- Covariates: Junior vs. senior; Acute vs. non-acute

Regression:

- Linear regression to determine the effects of covariates (Junior vs. senior; Acute vs. non-acute) on change in cortisol concentration over time
 - Separated into “death” and “survival” groups
 - Change in cortisol concentration will be established using the baseline reading of each participant on each day of the study (time point 1).
- Unpaired t-tests will be used to compare change in cortisol levels between the “death” group and the “survival” group at each time point.

Measure 2: State-Trait Anxiety Inventory (STAI)

- Analysis will be carried out in the same way as the cortisol measures with the STAI score taking the place of the change in cortisol concentration

Measure 3: Cognitive appraisal

- Mean cognitive appraisal ratios for each group (“death” and “survival”) at each time point will be calculated and subjected to a one-sample t-test to determine whether they are significantly different from 1.
- Unpaired t-tests will be used to compare the mean ratios of the “death” and “survival” groups at each time point.

Secondary Outcome 3: Valence of emotions

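### Video editing is the only method given for blinding the data analysts, and it cannot blind them; the claim is supported for the scenario raters only

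*Protocol*

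**What the plan says.** Protocol section 5 describes the study as an "investigator blinded, randomized, controlled, prospective trial". Section 6.3 says how the blinding is achieved: "Investigators performing data analysis and video raters will be blinded to group allocation by editing audio/video material", so that the end of the scenario, "with the occurrence of death or return of spontaneous circulation is not visible". One method is thus given for two roles, the people who analyse the data and the people who score the videos.

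Protocol section 7.3 then defines the comparison: "Group assignment (unexpected death, alive) will be used as the independent variable". The SAP does the same for the primary outcome and most secondary outcomes, "Independent variable: Death vs. survival", and has the cortisol regression "Separated into “death” and “survival” groups".

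Section 6 (Both Phases) says that scenarios and debriefings are both recorded for assessment by raters who do not know the allocation. Section 6.1.6 has the debriefings rated for quality by two expert raters. Section 6.4.2 says that debriefers ask participants directly how they felt about the simulated patient's death.

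**The concern.** A blinding claim is only as good as the step that delivers it. Here the step acts on video, whereas a statistical analyst works from a data set in which one column is the arm. Several outcomes in that data set (salivary cortisol, STAI, cognitive appraisal, emotions) do not come from video at all.

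At stake is the credibility of choices made during the analysis. Section 4.1 states a directional hypothesis, that death impairs retention, and the plan leaves some choices open that bear on the arm comparison. Section 7.1.1 defines the primary outcome as the difference between initial and retention test, while the SAP names the total score. For cortisol the SAP lists both an ANCOVA and unpaired t-tests. An analyst who knows which arm is which could settle such points with the direction of the result in view, and the trial could still be reported as having blinded analysts.

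**Working it through.** No figure in the documents bears on this point, so the check is a comparison of the sections.

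1. **Who is said to be blinded.** Section 6.3 lists data-analysing investigators and video raters as two groups joined by *and*, with one method for both.

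2. **What the method hides.** It hides the end of the scenario recording only. Section 6 (Both Phases) says the two versions run identically until the last two minutes and that the raters do not see the outcome. Section 6.1.2 drops post-resuscitation care from the checklist (18 points instead of 21) to protect the blinding. For scenario raters the method fits the purpose.

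3. **What the analyst handles.** The analyst handles a group variable, two stratification covariates and the outcome scores. Editing a recording changes none of these. For the non-video outcomes in section 7.1.2 the edit is irrelevant.

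4. **Whether another step masks the analyst.** Section 6.2 describes sealed opaque envelopes. These conceal the allocation until they are opened just before the scenario briefing and have no function afterwards. Neither document mentions coded arms, a key held by a third party, or an unblinding step after the analysis is locked. The analyst claim therefore rests on the video edit alone.

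5. **Whether the edit covers the debriefing recordings.** It applies to the end of the scenario. The debriefing comes after it and, under section 6.4.2, includes questions about the death. Each participant meets death once, at the initial test in the intervention arm and at the retention test in the control arm. A rater who hears the death discussed and knows which session is being rated therefore knows the arm.

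| Role | Does the stated edit mask the arm? | Other step described? |
|---|---|---|
| Scenario raters (primary and technical scores) | Yes, as a method | Post-resuscitation care not scored |
| Statistical analyst | No | None |
| Debriefing raters | No | None |
| Interview analysts | No | Transcripts anonymised, which removes identity, not content |

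**The case against.** **The plan may simply omit a coding step.** Any plan must name its arms to define the contrast, and a file coded A/B would fit the same ANCOVA. This stands. A reader might infer from the arm names in section 7.3 and the SAP that the analyst will certainly see unmasked data, so that analyst blinding does not exist. The documents do not say that. They show only that the stated method cannot produce the blinding and that no other is described.

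**The term investigators may mean the video scorers.** Section 6.1.2 calls the two raters investigators, and section 6 calls the use of the videos performance analysis. On that reading the edit is apt. The reading is possible but weaker, because section 6.3 lists the two roles separately and one would be redundant. Even if it is right, no statistical analyst is blinded and the sentence needs rewording.

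**The interviews.** Section 7.4 says that "ongoing preliminary analysis of the results gathered by the semi-structured interviews will lead to adaptation of the interviews". A reader might infer that the statistical analysts learn the arms this way. The documents do not support it: section 7.4 names no analyst, and section 6.1.5 has a research associate guide that work.

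**Type I error.** A reader might also want to attach an inflated error rate, from choosing between the change score and the total score. That inflation does not measure this defect. The smaller of two two-sided p-values is the same whichever arm is called A, so coding the arms would not prevent the choice. Fixing one dependent variable in advance would. That is a separate matter.

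**The exposure is limited.** The primary model has a named group factor and two named covariates, testing is two-tailed (section 7.2), and section 8.2 treats the findings as hypothesis generating. Two other open choices, curved or linear regression and ANCOVA or Pearson correlation, concern relations between outcomes, where knowing the arm gives little leverage. All of this stands and keeps the point modest.

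**Conclusion.** The point holds in a limited form. The stated method cannot blind the people who run the statistical models, and neither document gives another. The claim in section 6.3 is unsupported for analysts, as is the label in section 5 to the extent that it covers them. It is also unsupported for debriefing raters. This goes beyond missing detail, because a stated property is tied to a stated method that cannot deliver it.

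The size is modest and not quantified. The judgement-dependent step for the primary and technical outcomes is the scoring of scenarios, which the edit masks. That assessment assumes that the edit is carried out as described and that scenario raters do not see debriefing material before they score. The documents do not say whether the scenario raters and the debriefing raters are the same people.

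**What to change.** - **Section 6.3:** say that video editing blinds the scenario raters only.
- **Analyst, either:** supply a data set with arms coded A/B, with the key held by someone outside the analysis until the pre-specified primary and technical-skill models have been run and locked. The SAP can still name the arms to define the contrast; the programs use the codes.
- **Or:** withdraw the statement that analysts are blinded.
- **Debriefing raters and interview analysts:** state that they are not blinded, and whether the debriefing raters are the same people as the scenario raters.
- **Section 5:** make the blinding label match whichever option is taken.

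The cost is a few sentences in the protocol and SAP, plus one person outside the analysis to hold the key. The code might be guessed from secondary data such as the emotion scores, which is why the primary and technical-skill models should be locked first. Sample size, data collection and conduct do not change.

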6.4 Benefit and risk assessment

6.4.1 Benefits

By participating in this trial all participants will benefit from a short review of the actual resuscitation guidelines and will have the opportunity to improve their technical and non-technical skills in resuscitation and teamwork within two high-fidelity simulation sessions with video debriefing free of charge. Furthermore, as the safe environment of simulation and stress exposure training do effectively reduce state anxiety as well as performance anxiety during a real emergency situation and enhance performance during stress, participants will benefit from these positive effects during real clinical emergencies.

6.4.2 Risks

By creating a close to real setting and urging the participants to immerse into the scenario high-fidelity simulation is known to increase physiological and psychological stress throughout the simulation significantly above baseline levels. Especially with the occurrence of death, which is a potent stressor in the real clinical settings, emotions and stress might be aggravated. However, normal stress levels are reached at the end of the adjunct structured debriefings at common high stakes simulation sessions.

In order to detect any serious negative reactions to the scenarios, all scenarios will be debriefed by an experienced simulation instructor. The debriefers will specifically ask the subjects about their feelings and thoughts about the death of the “patient”, and will provide debriefing and coping strategies for dealing with death in the real life setting. Participants with overwhelming emotional responses, and who are emotionally troubled by the simulation experience, will be offered a voluntary professional referral to the counseling service of the University of Ottawa or the University of Toronto. In previous studies by one of the co-investigators ([name]) looking at highly stressful situations with over 400 front line workers and trainees, the subjects’ stress levels consistently returned to baseline levels at the end of the scenarios. Any residual negative emotions following such scenarios were consistently due to reflections on their own level of performance rather than on the emotional components of the scenarios themselves.

Furthermore there is a minimal risk of physical strain within this study. In order to minimize this risk, all participants will be familiarized with the mannequin prior to starting the first scenario.

7. ANALYSIS

7.1 Quantitative analysis

7.1.1 Primary outcome parameter

The difference in retention of non-technical skills for crisis management between the intervention and the control group (measured by the Ottawa Global Rating), specified as the difference in performance between the initial and the retention test, will be our primary outcome.

7.1.2 Secondary outcome parameters

Secondary outcomes will be (i) technical resuscitation skills (performance and retention) measured by the American Heart Association's Megacode Checklist (ii) stress including salivary cortisol, cognitive appraisal and STAI and (iii) valence of emotions.

7.2 Sample size considerations

A priori sample size calculation was performed on the basis of an estimated Cohen's *d* effect size of 0.8, which is considered large and acceptable for a teaching intervention.³³ We aim at a two-tailed level of significance of $p < 0.05$ and a power of 0.8. Using the recommended sample size estimation approach for ANCOVA³⁴ with an estimated r^2 of 0.12, derived by a previous, not now published trial ([name] et al, Learning crisis resource management: Practice versus observing, CAS 2013 Abstract 1653689, accessible at <http://www.cas.ca/English/AM-Abstracts-2013>), a number of 46 participants would be needed. In order to account for an estimated attrition rate of 20% we need to recruit 56 participants. G*Power for MAC (version 3.12, Düsseldorf, Germany) was used for sample size calculations.

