2. ABSTRACT

Background

High-fidelity simulation is an increasingly used teaching tool that is proven to be effective for learning. According to the literature, by gradually increasing stress and emotions, more effective learning can be achieved. However, allowing the simulated patient to “die”, as a deliberate stressor, is controversial. There is no previous research on the educational effect of letting a simulated patient die. We aim to evaluate the effects of simulated unexpected death on skill retention, stress levels, and emotions. We hypothesize that the occurrence of unexpected death will impact skill retention, and will be associated with higher stress levels and stronger emotions.

Methods

After Institutional Research Ethics Board approval, 56 residents and fellows of different medical specialties will be randomized to either the intervention (unexpected death) or control (survive) group. Participants from both groups will have to individually manage a simulated cardiac arrest crisis. In the intervention group, the scenario will end by the death of the simulated patient, whilst in the control group the simulated patient will survive. Each participant will be immediately debriefed by a trained instructor. Three months later, skill retention will be assessed in a similar scenario. Crisis management performance of all scenarios will be rated by 2 blinded raters. Biological stress, cognitive appraisal, and emotions will be measured during both scenarios.

Implications

The impact of simulated unexpected death on skill retention of residents and fellows will provide instructors with evidence to optimize scenario design and approach the role of stress and emotions in simulation-based education.

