6.2 Randomization

In order to create groups of participants that are similar in regards of their baseline characteristics and in order to increase the power of our study we will use the approach of stratified randomization to allocate the participants to the intervention and control group. In order to keep the number of strata and the resulting covariates small we will stratify the participants regarding their level of training (PGY1 – PGY3 residents, vs. PGY4 – PGY 5 residents and fellows), their likelihood of providing acute care (acute care specialties will include anesthesia, emergency medicine and critical care trained personnel). Thereafter computer block randomization will be performed using the algorithm provided at www.randomization.com for all subgroups. Participants will be assigned to the

intervention (initial test ending with asystole) and control (initial test ending with sinus rhythm) groups in a 1:1 ratio. To ensure even allocation to the intervention and control group blocks of 4 participants will be predefined. Sealed, numbered, opaque envelopes, containing the random allocation, will be opened after the resting period immediately before scenario briefing begins.

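### Section 7.2: recruiting 56 with 20% attrition leaves about 45 completers, not the 46 stated as needed; the power effect is about one percentage point

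*Protocol*

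**What the plan says.** Protocol section 7.2 sets out the calculation in three steps.

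- **Inputs:** a Cohen's d "effect size of 0.8, which is considered large and acceptable for a teaching intervention", a "two-tailed level of significance of $p < 0.05$ and a power of 0.8", and an ANCOVA approach "with an estimated r^2 of 0.12".
- **Requirement:** "a number of 46 participants would be needed".
- **Recruitment:** "In order to account for an estimated attrition rate of 20% we need to recruit 56 participants".

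The abstract repeats the last figure as the number to be randomized: "56 residents and fellows of different medical specialties will be randomized". Section 6.2 allocates participants to the "groups in a 1:1 ratio". Neither document states the formula used to get from 46 to 56, or says whether the 20% is a share of those recruited or of those needed. The SAP has no sample-size section.

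**The concern.** An attrition rate ordinarily means the share of enrolled participants who are lost. On that meaning the number to recruit is the number needed divided by one minus the rate. Multiplying the number needed by one plus the rate gives too few. The 56 in section 7.2 looks like the second calculation, and it falls short of the target it is said to protect.

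Attrition bears directly on the primary outcome. That outcome is the change in the Ottawa Global Rating score from the initial test to the retention test three months later, so a participant who does not return has no primary outcome value. A reader comparing actual dropout with the plan would regard 11 losses from 56 (19.6%) as within the stated 20%, yet 11 losses already leave 45. At stake is the accuracy of a stated planning figure, with at most a slight loss of power.

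**Working it through.** **Inputs, all from Protocol section 7.2:** d = 0.8; two-sided alpha 0.05; power 0.80; r² = 0.12, so the variance factor is 1 − 0.12 = 0.88; attrition 20%; 46 needed; 56 recruited. The 1:1 allocation is from section 6.2.

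**1. Reproducing the 46.** A two-sample t-test with d = 0.8 (noncentral t) has power 0.791 at a total of 50 and 0.807 at 52, so 52 are needed without covariates. Applying the ANCOVA factor gives 52 × 0.88 = 45.76, rounded up to 46. Working directly with the adjusted effect, 0.8 / √0.88 = 0.853, the smallest even total with power of at least 0.80 is again 46. The requirement is sound.

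**2. The attrition step.**

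- Expected completers from 56: 56 × (1 − 0.20) = 44.8.
- Recruits needed to expect 46: 46 / (1 − 0.20) = 57.5, rounded up to 58. Check: 58 × 0.8 = 46.4.
- Adding 20% to the requirement: 46 × 1.20 = 55.2, rounded up to 56, which matches the printed figure.
- Attrition that 56 can absorb while leaving 46: (56 − 46) / 56 = 10/56 = 17.9%.
- One more loss: 11/56 = 19.6%, leaving 45.

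The gap is 2 recruits, or about 1 completer (46 − 44.8 = 1.2).

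**3. Effect on power.** Noncentral t with d = 0.853 and N − 4 degrees of freedom (intercept, group and two binary covariates):

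| Completers | Power |
|---|---|
| 46 | 0.807 |
| 45 | 0.798 |
| 44.8 (expected) | 0.796 |
| 44 | 0.788 |

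Power of exactly 0.80 is reached at 45.3 completers (45.2 with N − 2 degrees of freedom). The d detectable with power 0.80 is 0.793 at 46 completers and 0.804 at 44.8.

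**4. Allowing for chance in dropout.** Assume each participant drops out independently with probability 0.20; the documents do not state this. The chance of at least 46 completers is then 0.42 from 56 recruits and 0.63 from 58. Power averaged over the same dropout distribution is 0.794 from 56 and 0.808 from 58, a difference of 1.4 percentage points.

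**The case against.** The strongest reply is that nothing depends on the difference. The 46 is itself rounded up, and power of exactly 0.80 needs only 45.3 completers. Against the power target, the expected shortfall is therefore about half a participant (45.3 − 44.8 = 0.5), and 0.796 rounds to 0.80. Effect size, r² and attrition are all estimates, and modest error in any of them could outweigh this gap. With the normal approximation the total is 43.2, or 44 at 22 per arm, and 44 / 0.8 = 55, so 56 would cover 20% attrition. If the 20% is read as a share of the 46, 56 is also enough. No rule in either document is tied to the 20%, and section 8.2 already warns that the study may be underpowered.

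The points about size stand, and they keep this minor. The chances of reaching 46 should not be read as evidence of a power deficit, because even 58 recruits miss 46 more than a third of the time; the averaged power is the fairer measure.

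The rest does not reconcile the text. The protocol prints 46, not 44. A rate applied to the 46 is not the usual meaning of attrition, and the abstract makes 56 the number randomized. The general caution in section 8.2 does not correct a specific figure in section 7.2.

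**Conclusion.** The concern holds as a minor arithmetic inconsistency. On the ordinary meaning of attrition, as a share of those recruited, 56 does not deliver the 46 completers stated as needed: it delivers about 45, and 58 would be required. The printed 56 is consistent with adding 20% to 46, but with no formula given that remains an inference.

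Under the protocol's own d of 0.8 and r² of 0.12, expected attrition takes power from 0.807 to 0.796, about one percentage point. The trial is not materially underpowered for this reason. The conclusion rests on the printed figures and on that reading of attrition; the power values also rest on the protocol's effect size and r² being right.

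**What to change.** Reword the recruitment sentence in section 7.2 so that its figures agree, and keep 56. Either of these would do:

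- recruiting 56 allows for up to 17.9% attrition (10 of 56) while retaining 46 completers; or
- with 20% attrition, 56 recruits leave about 45 completers, with power of about 0.796 under the stated assumptions.

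Giving the inflation formula in the same sentence would remove any doubt about which denominator the rate applies to.

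The cost is one sentence. No further participants are needed, and the abstract, the randomization blocks and the analysis stay as they are.
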